6.1. Intent-to-Treat Population

The intent-to-treat (ITT) population will consist of all randomized subjects. All primary and secondary efficacy endpoints will be analyzed based on the ITT population. All analyses on the ITT population will be analyzed under the treatment group “as randomized”.

6.2. Safety Population

The safety population will comprise all randomized subjects who receive at least 1 dose of study drug. All safety data will be summarized based on the safety population under the treatment group “as treated”.

6.3. Proof of Exposure Analysis Population

The proof of exposure (POE) analysis population will include all subjects in the safety population who provide at least 1 measurable post-baseline evaluable drug concentration value.

6.4. Per-Protocol Population

The Per-Protocol (PP) population will consist of all subjects in the ITT population who have no major protocol deviations that would have a significant effect on the efficacy of the study treatment (see [Section 6.5](#)). Only primary and selected secondary endpoints will be analyzed using the Per-Protocol Population, under the treatment group as randomized.

6.5. Protocol Deviations

Protocol deviations will be recorded by the Clinical Research Associate (CRA) in the Clinical Trial Management System (CTMS). All protocol deviations will be categorized by the associated deviation type and will be assessed individually on a regular basis on whether they are major or minor. Details can be found in the Protocol Deviation and Non-compliance Management Plan.

Major protocol deviations that are analysis relevant lead to an exclusion of the subject from the per-protocol population. A case by case decision regarding exclusions of subjects from the per-protocol analysis will be made in a blind data review meeting (BDRM) which will take place prior to unblinding the study. The criteria for exclusion from the Per-Protocol Population will be specified in the BDRM Preparation Plan. Only major protocol deviation which have a significant effect on the efficacy will result in exclusion from the Per-Protocol Population.

Individual deviations (major and minor) will be presented in a data listing on the ITT population. A summary table for number and percentage of subjects with major protocol deviation will be generated by type of deviation and treatment group for the ITT population.

This document is confidential.

Protocol deviations incurred as a direct result of the COVID-19 pandemic should be specifically recorded and presented as a COVID-19 deviation. The number and percentage of subjects with major (including COVID-19) deviation will be provided by type of deviation and treatment group for the ITT population.

All protocol deviations will be listed.

This document is confidential.

7. Estimands

The primary efficacy endpoints will be evaluated and assigned to treatment at the time of randomization based on ITT Population. The estimand is defined to address the scientific question relevant to subjects who are able to complete treatment with a response assessment without further medication being required, other than permitted medication.

An intercurrent event is an event which occurs after start of treatment and thus complicates the description and interpretation of treatment effects. [Table 7-1](#) below lists potential intercurrent events and the strategy to deal with them for the estimand. The estimands for endpoints are defined in [Table 7-2](#).

[Table 7-2](#)

Table 7-1: List of Intercurrent Events

Intercurrent Event	Strategy to Deal With Intercurrent Event Within Analysis	Assessment of Subject
Treatment discontinuation	While on Treatment Strategy	Any data collected after a treatment discontinuation will be censored
Use of prohibited medication	While on treatment strategy	Any data collected after a use of prohibited medication will be censored

Table 7-2: Estimands for primary Endpoint

Endpoints	Estimands
Time to relapse meeting at least 1 of the defined criteria*	Treatment: randomized treatment with subcutaneous injections of nemolizumab or placebo at Week 0, 4, 8, 12, 16, and 20
	Population: ITT population
	Endpoint: Time to relapse meeting at least 1 of the defined criteria
	Intercurrent events: Time to relapse will be censored at the last observation prior to treatment discontinuation or use of prohibited medication

This document is confidential.

Endpoints	Estimands
	Summary measure: Hazard ratio of nemolizumab and placebo

*the time to relapse which is defined as meeting at least 1 of the following criteria:

- Increase in (weekly average of the) PP NRS score ≥ 4 points from baseline
- Increase in IGA score ≥ 2 points from baseline

This document is confidential.

8. General Aspects for Statistical Analysis

8.1. General Methods

- All data will be listed, and summary tables will be provided.
- Unless otherwise specified, summaries will be presented for each treatment, if indicated, by visit.
- Continuous variables will be summarized using the number of observations (n), mean, standard deviation (SD), median, minimum and maximum. Categorical variables will be summarized using number of observations (n), frequency and percentages of subjects
- Unless otherwise stated, all statistical tests will be two-sided and conducted at the 5% level; all presented confidence intervals (CIs) will be two-sided 95% CIs.

8.2. Key Definitions

The 24-week **treatment period** is defined as Day 1/Baseline to Week 24. If early discontinued during treatment period, it is defined as the period until 4 weeks (<=28 days) after last dosing date or early termination date whichever is earlier.

The **Baseline value** is defined as the last non-missing value before the first dose of study drug. In case that the date of first injection is not available, the date of randomization is considered.

For diary data (PP NRS, SD NRS), the Baseline values will be week 52 value from LTE trial.

The **date of first treatment** is defined as the date of first injection of study drug.

The **date of last treatment** is defined as the date of last injection of study drug.

Study day is defined as the number of days from the date of first treatment (randomization date if not treated) and will be calculated as follows:

- If the event date \geq date of first treatment, then study day = event date – date of first treatment + 1. Treatment Day 1 is therefore defined as the day of first treatment.
- If the event date $<$ date of first treatment, then study day = event date - date of first treatment.
- If subject is randomized, but not treated, then study day = event date - date of randomization.

A subject's **date of last participation** in the trial is the last date of contact.

Only the **subjects infected by COVID-19** during study participation will be considered subjects with COVID-19 infection.

This document is confidential.

8.3. Missing Data

When analyses are not based on OC, the primary method to impute the missing values will be as follows:

Continuous Endpoints: For continuous secondary endpoints during treatment period, the MMRM approach will be used to handle the missing data.

Binary Endpoints: For binary secondary endpoints during treatment period, missing data will be imputed to failure.

Adverse events and concomitant medications/procedures: Missing assessment times will have imputed times for the purposes of assessing treatment emergence for AEs or classifying medications/procedures into prior/concomitant. However, the assessment date and time (start date, stop date, and time if collected from CRF) without imputation will be presented in the listings.

For the start of a concomitant medication/procedure or AE:

- Only the year is reported: If the subject received the first study drug dose in the year reported, then the date of the first dose of study drug will be used as the start date; otherwise, January 1 of the year reported will be used as the start date.
- The month and year are reported: If the subject received the first study drug in the month and year reported, then the date of the first dose of study drug will be used as the start date; otherwise, the first day of the month and year will be used as the start date.
- The time is collected but missing: If the start date is the same as the date the subject started receiving study drug, then the time of the first dose of study drug will be used as the start time; otherwise, 00:00 will be used as the start time.

For the end of a concomitant medication/procedure or AE:

- Only the year is reported: The earlier between December 31 of the year reported and the date of the last study contact with the subject will be used as the stop date.
- The month and year are reported: The earlier between the last date of the month and year reported and the date of the final contact with the subject will be used as the stop date.
- The time is collected but missing: 23:59 (or 23:59:59 if collected up to seconds) will be used as the stop time.

This document is confidential.

If an AE has the start date completely missing and the stop date on/after the first dose date of study drug, this AE will be considered as treatment emergent (TEAE).

If a medication/procedure has the stop date completely missing, this medication/procedure will be considered as ongoing and concomitant. If the start date of a medication/procedure is completely missing and impossible to identify different by stop date, this medication will be considered as concomitant.

8.4. Visit Windows

Efficacy by-visit summaries will use the analysis visit. All visits including unscheduled and early termination visits will be windowed based on the analysis visit window in [Table 8-1](#) which is based on study day. If multiple measurements are taken within the same window, the one taken closest to the target study day will be used for the analysis. If there are multiple measurements with same difference from target day, the later assessment should be used for the analysis.

Table 8-1: Analysis Visit Window

Analysis Visit	Target Study Day	Visit Window (IGA)	Visit Window (DLQI)
Baseline	1	≤ 1	≤ 1
Week 4	29	2 to 42	N/A
Week 8	57	43 to 70	N/A
Week 12	85	71 to 98	N/A
Week 16	113	99 to 126	2 to 140
Week 20	141	127 to 154	N/A
Week 24	169	155 to 210	141 to 210
Week 32 Follow-up	225	>211	N/A

All daily diary efficacy data will be classified into analysis visits as described in [Table 8-2](#) considering the data during the 7 days immediately preceding the target day of analysis visit.

Analysis visit of diary (ePRO) data will be defined depending on the data collection as below.

Consecutive daily assessment:

For the evening assessments (PP NRS), the daily data collected up to Week 24 will be classified into analysis visits considering the data during the 7 days immediately preceding the target study day of analysis visit. Similarly, for the morning assessment (SD NRS, morning sleep diary), the 7 days data up to the target study day will be classified into analysis visit. Details of the analysis visit window are in [Table 8-2](#) below.

This document is confidential.

Table 8-2: Analysis Visit Window for Evening and Morning Assessments

Analysis Visit	Target Study Day of Analysis Visit	Visit Window for evening assessment (PP NRS, AP NRS)	Visit Window for morning assessment (SD NRS, morning sleep diary)
Baseline	1	-7 to -1	-6 to 1
Week 1	8	1 to 7	2 to 8
Week 2	15	8 to 14	9 to 15
Week 3	22	15 to 21	16 to 22
Week 4	29	22 to 28	23 to 29
Week 5	36	29 to 35	30 to 36
Week 6	43	36 to 42	37 to 43
Week 7	50	43 to 49	44 to 50
Week 8	57	50 to 56	51 to 57
Week 9	64	57 to 63	58 to 64
Week 10	71	64 to 70	65 to 71
Week 11	78	71 to 77	72 to 78
Week 12	85	78 to 84	79 to 85
Week 13	92	85 to 91	86 to 92
Week 14	99	92 to 98	93 to 99
Week 15	106	99 to 105	100 to 106
Week 16	113	106 to 112	107 to 113
Week 17	120	113 to 119	114 to 120
Week 18	127	120 to 126	121 to 127
Week 19	134	127 to 133	128 to 134
Week 20	141	134 to 140	135 to 141
Week 21	148	141 to 147	142 to 148
Week 22	155	148 to 154	149 to 155
Week 23	162	155 to 161	156 to 162
Week 24 ^a	169	162 to 175	163 to 176
Early Termination*	UN	7 days prior until Early termination visit (excluding early termination visit date)	6 days prior until early termination visit (including early termination visit date)

^a First 7 days data available will be used for weekly average calculation.

*For subjects with early termination, if weekly average is not available based on the slotting, additional analysis window was added and will be assigned to the week based on the slotting above. i.e., if subject

This document is confidential.

early terminated day 142, and week 21 is not available, the new window defined will be used to determine the weekly average at that week.

Safety and pharmacokinetics data will not be windowed for by-visit summary. i.e., scheduled visit data will be used for analysis.

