### 14.3 Efficacy Analysis

A summary based on observed case (OC) will be provided for all primary and secondary efficacy endpoints. For OC, no data will be imputed.

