If a subject meets the criteria for relapse at any point, the subject will exit the study and re-enter the LTE study (see [Figure 4-1](#)). Subjects who exit the study before Week 24 should complete an early termination (ET) visit. Subjects who complete the study through Week 24 are eligible to re-enroll in the LTE study.

Subjects who prematurely discontinue study drug for reasons other than relapse will be encouraged to complete the scheduled study visits. These subjects will only be eligible for re-enrollment in the LTE study if they continue with study visits through Week 24.

Subjects who discontinue the study for reasons other than relapse before Week 24 or who will not continue nemolizumab treatment in the LTE study should complete a follow-up visit, 12 weeks (± 7 days) after the last study drug injection.

[figure not shown]
Follow-up Period

This document is confidential.

A follow-up visit will be conducted 8 weeks (± 7 days) after completing the treatment period and/or 12 weeks (± 7 days) after the last study drug injection for all subjects who will not continue nemolizumab treatment in the LTE study. Twelve weeks corresponds to approximately 5 half-lives of nemolizumab when administered subcutaneously Q4W at the doses used in this study.

An overview of the study is presented in [Figure 4-2](#).

Figure 4-2: Study Design

*Clinical responder is defined as a subject with an Investigator Global Assessment (IGA) score= 0 or 1 and improvement in Peak Pruritus Numeric Rating Scale (PP NRS) score of ≥ 4 points from baseline of the lead-in study at Week 52 visit of the LTE study. Note: Lead-in study baseline is defined as baseline PP NRS score in the Phase 3 studies RD.06.SPR.202685 or RD.06.SPR.203065 for subjects who rolled over into the LTE from these studies. For subjects who entered the LTE study from the Phase 2 study RD.03.SPR.115828, the baseline PP NRS score at entry into the LTE study RD.06.SPR.202699 will be used.

** Relapse is defined as an increase in weekly average of PP NRS score ≥ 4 points from baseline or an

This document is confidential.

increase in IGA score ≥ 2 from baseline at any point during the study. Subjects who relapse at any point during the treatment period or who complete through Week 24 are eligible for LTE re-entry.

Abbreviations: BL = baseline; LTE = long-term extension; R = randomization; W = week.

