ACT = Asthma Control Test; ADA = anti-drug antibody; AE = adverse event; DLQI = Dermatology Life Quality Index; ECG = electrocardiogram; ET = early termination; FSH = follicle-stimulating hormone; FU = follow-up; HIV = human immunodeficiency virus; ICF = informed consent form; IGA = Investigator Global Assessment; LTE = long-term extension; PEF = peak expiratory flow; POE = proof of exposure; PP NRS= peak pruritus numeric rating scale; SD NRS= sleep disturbance numeric rating scale; TB = tuberculosis; UPT = urine pregnancy test; V = visit; W = week.

- After signing the ICF, all subjects will be evaluated for study participation, based on eligibility criteria. The Week 52 study assessments from the LTE lead-in study RD.06.SPR.202699 will be used as baseline assessments for the current study.
- Subjects who relapse or discontinue prematurely (before the Week 24 visit) should complete an ET visit. If the subject discontinues for reasons other than relapse before Week 24, or will not continue with nemolizumab treatment in the LTE study, a follow-up visit should also be completed, 12 weeks (±7 days) after the last study drug injection.
- Assessments to be conducted at the unscheduled visit depend on the reason for the visit. POE and ADA analyses should only be performed at unscheduled visits that are conducted for safety reasons when safety labs are collected for the management/monitoring of an AE. When a series of unscheduled visits is needed for the monitoring of the same AE, the POE and ADA collection is not required if already done at the first unscheduled visit of the series. Additional collection of samples for POE and ADA analysis should be performed per Investigator's judgment.
- PP NRS to be recorded by subjects once daily in the evening. SD NRS to be recorded by subjects once daily in the morning and if possible, within 1 hour of getting out of bed.
- Patient-reported outcome assessments and designated safety measurements (including AE and concomitant therapies/procedures assessments) should occur before Investigator assessments, laboratory sample collections, and study drug administration.
- Subjects with a history of asthma will complete the ACT testing at all visits. Subjects with a new (de novo) diagnosis of asthma will complete the ACT testing beginning from de novo diagnosis and at all subsequent scheduled visits.

This document is confidential.

Statistical Analysis Plan for Interventional Studies

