5.2. Secondary Efficacy Endpoints

The secondary efficacy endpoints are as follows:

- Proportion of subjects with increase in PP NRS score ≥ 4 points from baseline at each scheduled visit
- Proportion of subjects maintaining IGA success, defined as IGA score of 0 (clear) or 1 (almost clear) at each scheduled visit
- Proportion of subjects with increase in IGA ≥ 2 points from baseline at each scheduled visit
- Absolute and percent change from baseline in PP NRS at each scheduled visit
- Absolute and percent change from baseline in Sleep Disturbance Numeric Rating Scale (SD NRS) at each scheduled visit
- Change from baseline in DLQI at Week 16 and Week 24

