10.2.4. Dermatology Life Quality Index

The DLQI is a validated 10-item questionnaire covering domains including symptoms/feelings, daily activities, leisure, work/school, personal relationships, and treatment.

The subject will rate each question ranging from 0 (not at all) to 3 (very much). The DLQI total score is calculated by summing each questionnaire. Total score will have a maximum score of 30 and a minimum of 0. The higher score indicated a poorer quality of life.

DLQI will be collected at Baseline, Week 16, Week 24 and Early Termination. DLQI total score will be summarized as a continuous variable using OC on the ITT Population. Absolute change and percentage change from Baseline in DLQI total score will also be summarized.

Absolute change from Baseline in DLQI will be analyzed using ANCOVA based on OC, including treatment group dose regimen as factors with baseline value as covariate. The least squares means (LSMeans), standard error of LSMeans, and 95% CI for change from baseline, as well as the difference in LSMeans between the treatment groups, the two-sided 95% CI, and associated p-value will be presented. Percentage change from Baseline in DLQI will not be analyzed because of the small sample size and potential high skewness of the data.

This document is confidential.

11. Pharmacokinetics

The serum concentration of Nemolizumab will be assessed at Baseline, Week 24 and Early Termination visit. PK analyses are required during any unscheduled visit conducted for safety reasons. As a guideline, PK samples should be collected at approximately the same time of day throughout the study, to the extent possible, before study drug injection (pre-dose samples).

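### The DLQI Week 16 window (Days 2 to 140) files early relapse-day values as Week 16, and the observed-case Week 24 analysis omits those subjects, so Week 24 can understate worsening after withdrawal

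*SAP*

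**What the plan says.** The endpoint in SAP 5.2 is "Change from baseline in DLQI at Week 16 and Week 24". SAP 10.2.4 says "DLQI will be collected at Baseline, Week 16, Week 24 and Early Termination"; the schedule also allows it at unscheduled visits.

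SAP 8.4 assigns assessments to analysis visits by study day: "All visits including unscheduled and early termination visits will be windowed based on the analysis visit window in" Table 8-1. DLQI has two post-baseline windows there: Week 16, Days 2 to 140 (target Day 113), and Week 24, Days 141 to 210 (target Day 169). For duplicates, "If multiple measurements are taken within the same window, the one taken closest to the target study day will be used for the analysis".

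On relapse, SAP 4.1 says "If a subject meets the criteria for relapse at any point, the subject will exit the study and re-enter the LTE study". A footnote to the schedule in SAP 4.6 adds "Subjects who relapse or discontinue prematurely (before the Week 24 visit) should complete an ET visit".

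On analysis, SAP 10.2.4 says "Absolute change from Baseline in DLQI will be analyzed using ANCOVA based on OC", and Protocol 14.3 says of observed cases (OC) "For OC, no data will be imputed". SAP 10.2 applies MMRM to PP NRS and SD NRS only. Protocol 14.3.2 lists DLQI under MMRM as well. SAP section 14, which records changes from the protocol, does not mention the omission.

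**The concern.** An early relapser normally has one post-baseline DLQI, taken on the day of exit. The plan counts it at Week 16 whatever the day, and the subject is then missing at Week 24. The two time points of one endpoint therefore rest on different subjects, selected by outcome, and the Week 16 label is untrue for some of them. IGA from the same ET visit goes to its own week, and PP NRS is slotted week by week.

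The trial exists to describe what happens after withdrawal, and early relapsers carry most of that information. If they count at Week 16 and not at Week 24, the Week 24 mean can look too favourable in the arm with more relapses, and the treatment difference can shrink between the two visits for reasons unrelated to quality of life.

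**Working it through.** **1. The window.** The midpoint of the two DLQI targets is (113 + 169)/2 = 141, so Week 16 runs to Day 140 and Week 24 starts on Day 141. This reproduces Table 8-1. The Week 16 window is 140 − 2 + 1 = 139 days wide and reaches 111 days before target and 27 days after it.

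**2. Where an ET visit falls.**

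| ET study day | IGA visit | DLQI visit | Days before Day 113 |
|---|---|---|---|
| 29 | Week 4 | Week 16 | 84 |
| 57 | Week 8 | Week 16 | 56 |
| 85 | Week 12 | Week 16 | 28 |
| 136–140 | Week 20 | Week 16 window, but the scheduled Week 16 value is nearer, so the ET value is unused | – |
| 141–146 | Week 20 | Week 24 | – |

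The closest-to-target rule does not help in the first three rows, because there is normally no second DLQI to choose.

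**3. Illustration of size.** The documents give no relapse rate or DLQI change, so these inputs are assumptions: placebo relapse p by Week 24 at constant hazard over six visits; DLQI change +8 at relapse and +1 otherwise; half of Week 20 relapse visits on or after Day 141. Cumulative relapse at visit k is 1 − (1 − p)^(k/6).

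For p = 0.5:
- Relapsed by Week 12: 1 − 0.5^(3/6) = 0.293. By Week 16: 0.370. At Week 20: 0.069. At Week 24: 0.061.
- Week 16 mean: 0.370 × 8 + 0.630 × 1 = +3.59.
- Week 24 contributors: 0.034 + 0.061 + 0.500 = 0.596 of the arm. Mean: (0.0956 × 8 + 0.5 × 1)/0.596 = +2.12.
- Every relapser kept at the relapse value: 0.5 × 8 + 0.5 × 1 = +4.5.

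| p | Week 16 | Week 24 | All relapsers kept |
|---|---|---|---|
| 0.3 | +2.48 | +1.60 | +3.1 |
| 0.5 | +3.59 | +2.12 | +4.5 |
| 0.7 | +4.86 | +2.85 | +5.9 |

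With about 20 per arm (40 in Protocol 14.1 and SAP 4.3), 0.293 × 20 ≈ 6 placebo subjects would have a Week 16 value from Weeks 4 to 12. SAP 4.1 says about 100 subjects; 50 per arm would give about 15.

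**4. Treatment difference.** Assume +8 at relapse, 0 otherwise, Week 20 visits on Day 141, and relapse of 60% on placebo and 10% on nemolizumab. Nemolizumab minus placebo is 0.54 − 3.66 = −3.11 (unrounded) at Week 16 and 0.28 − 2.11 = −1.83 at Week 24, against 0.8 − 4.8 = −4.00 with all relapsers kept.

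**5. When the apparent recovery does not occur.**
- Late relapse (per-visit probabilities 0, 0.05, 0.05, 0.10, 0.20, 0.20; +8 and 0): the mean rises from +1.50 to +2.88, against +3.84 with all kept.
- Worsening in non-relapsers (p = 0.5; +1 at Week 16, +3 at Week 24): Week 24 is (0.0956 × 8 + 0.5 × 3)/0.596 = +3.80, above +3.59, against 0.5 × 8 + 0.5 × 3 = +5.5 with all kept.

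**6. Effect of only narrowing the windows** (Week 16 = Days 99 to 126, Week 24 from Day 155; p = 0.5):
- Week 16: (0.077 × 8 + 0.630 × 1)/0.707 = +1.76, down from +3.59.
- Week 24: (0.061 × 8 + 0.5 × 1)/0.561 = +1.76, down from +2.12.
- At p = 0.3, Week 24 falls from +1.60 to +1.40. At p = 0.7, it falls from +2.85 to +2.27.

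**The case against.** The best defence is that the wide window is useful. It keeps every relapser through Week 16 in the Week 16 analysis at the relapse value, so under the model above +3.59 is the all-relapsers-kept mean at that visit. That stands: the Week 16 fault is one of timing and labelling, not of lost subjects.

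A reader might infer that the window causes the loss at Week 24. The documents do not support this. Relapsers are absent because they leave for the long-term extension and the analysis is observed-case, and any by-visit window would leave them out. The existing Week 24 window even retains Week 20 relapsers seen from Day 141, whom a window opening on Day 155 would drop.

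A reader might also infer that a false recovery is built in. It is not. It needs mostly early relapse and fairly stable DLQI in non-relapsers, and nothing in the documents fixes either.

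It may be said that the protocol already has a remedy in the DLQI MMRM and optional multiple imputation. Protocol section 14 lets the SAP prevail where they differ, and the SAP's analysis table and table index list only ANCOVA for DLQI. SAP 8.3 names MMRM for continuous secondary endpoints only where the analysis is not observed-case, and no such DLQI analysis is listed.

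Finally, DLQI is secondary in a small study with no formal sample size calculation. That limits the weight of the point but does not remove it.

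**Conclusion.** The point holds in this form. Week 16 DLQI combines relapse-day values from as early as Week 4 with true Week 16 values. Week 24 DLQI describes only subjects still in the study at Day 141. No listed DLQI analysis keeps early relapsers at the end of treatment.

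In every scenario computed, the Week 24 observed mean lay below the mean with all relapsers kept: +2.1 against +4.5 in the 50% case. This direction requires DLQI to have worsened more in relapsers than in non-relapsers. The comparator holds each relapser at the exit value; it is a reference summary, not the truth at Week 24. An apparent gain from Week 16 to Week 24 (1.5 points in that case) is possible but conditional. All sizes rest on assumed relapse rates, relapse timing and DLQI changes. The primary analysis is unaffected.

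**What to change.** Before unblinding:

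1. Add one ANCOVA on change from baseline in the last on-study DLQI, using the ET value for subjects who exit early and the Week 24 value otherwise, with the same factors and baseline covariate as the planned model.
2. In the Week 16 summary, show ET DLQI values taken outside Days 99 to 126 as ET, by actual study day, so that the reader can see how many there are and when they were taken.
3. Reconcile the DLQI MMRM: either restore it in SAP 10.2 or record and justify its removal in SAP section 14.

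Do not simply narrow the Table 8-1 windows, since that removes more relapsers from both visits.

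The cost is one or two extra tables and no new data collection. The last on-study estimate mixes assessment times and must be labelled accordingly; it supplements the by-visit results and does not estimate change at Week 24.
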